### **Exclusion criteria**

- 1) Patients with histological diagnosis different from parosteal osteosarcoma

### **MATERIAL AND METHODS**

We will retrieve from the database of the Rizzoli institute all the cases with a histological diagnosis of parosteal osteosarcoma from 01Jan1900 to 31Jul2018.

We aspect to find approximately 220 cases.

We will review all the medical records, radiological imaging, and histological data of these cases.

### **STATISTICS**

To the case series will be applied a descriptive statistic.

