## BACKGROUND

Parosteal osteosarcoma is a low-grade, malignant bone tumor arising usually on the metaphyseal surface of a long bone. It accounts for about 4% of all osteosarcomas and although rare, it is the most common type of osteosarcoma of the surface of bone (1). Around 15-25% of cases reported in literature showed high-grade spindle cell areas, indicating progression to high-grade sarcoma (dedifferentiation) that may resemble conventional osteosarcoma or undifferentiated spindle or pleomorphic sarcoma (2-5). This progression (dedifferentiation) may be seen at the time of the first diagnosis or, more often, at the time of recurrence. The medullary involvement of the tumor evaluated on CT and MRI and confirmed on histological specimen is another important feature of parosteal osteosarcoma that has been described in a variable percentage of cases reported in literature (range, 28-48% of series published) (2-5). The presence of the medullary involvement could change the surgical treatment, even if it does not seem to have an impact on survival and on local recurrence or metastases, at difference to the presence of progression (dedifferentiation) areas and of inadequate surgical margins that are the most important prognostic factors in parosteal osteosarcoma reported in literature (1-5). This data should be verified in a wide series of parosteal osteosarcoma with an adequate follow-up, because the case series but two, reported in literature, are limited in terms of number of cases and of time of follow-up (4,5).

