## OBJECTIVE OF THE STUDY

The aim of the present study is to review all the cases with a diagnosis of primary parosteal osteosarcoma treated at the Rizzoli Institute from 1900 up to 31 July 2018, retrospectively.

The study will exam all the clinical, radiological, and histological features of this tumor with regard importance of medullary involvement, the types of treatment, the status of surgical margins, the presence of progression (dedifferentiation) areas and the relationship of these factors to individual outcome.

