## POPULATION

### Inclusion criteria

- 1) Male and female patients treated at Rizzoli Institute from 01 Jan 1900 to 31 Jul 2018
- 2) Diagnosis of parosteal osteosarcoma

- 3) Written informed consent prior to any study-specific analysis and/or data collection

According to the Italian “*Autorizzazione generale n. 9/2016 al trattamento dei dati personali effettuato per scopi di ricerca scientifica*” of the Privacy Tutor (and the corresponding regulation in the other participating countries) the informed consent is not required to be obtained by the deceased subjects, as long as all the other enrolment criteria are met and the study has been approved by the Ethic Committee (refers to INFORMED CONSENT section)

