### **ENROLLMENT PROCEDURE**

Patients considered eligible will be included in the study, after providing a written informed consent.

Since we will include cases of several decades ago, and due to the high incidence of mortality of the disease under investigation, it would be possible that some eligible subjects will be deceased.

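### The aim is to relate four factors to outcome, but the only analysis commitment is descriptive statistics, which crude percentages would satisfy, and the protocol does not say when dedifferentiation is scored

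*Protocol*

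**What the plan says.** The Objective section names four factors (medullary involvement, type of treatment, surgical margins, dedifferentiation) and sets out to examine "the relationship of these factors to individual outcome". It does not define outcome.

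The Background supplies the reason. Of medullary involvement it reports that "it does not seem to have an impact on survival and on local recurrence or metastases", in contrast to dedifferentiation and inadequate margins, which it describes as the main prognostic factors. It then adds: "This data should be verified in a wide series of parosteal osteosarcoma with an adequate follow-up". On timing, it says that dedifferentiation "may be seen at the time of the first diagnosis or, more often, at the time of recurrence".

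The Statistics section is a single sentence: "To the case series will be applied a descriptive statistic". The population is "Male and female patients treated at Rizzoli Institute from 01 Jan 1900 to 31 Jul 2018", with no minimum follow-up. Material and Methods expects about 220 cases.

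**The concern.** The aim is about association with outcome over time, whereas the analysis commitment is a general word. A table of crude event percentages by factor would fulfil the Statistics section and still leave the aim unanswered, for three reasons.

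- **Censoring.** Patients treated shortly before the cut-off and patients treated decades earlier would count equally in the denominator, so a crude percentage depends on length of follow-up as well as on risk.
- **Circularity.** No section says whether dedifferentiation means status at first diagnosis or at any time. If it means any time, every case discovered at recurrence has recurred by definition, and the outcome becomes part of the factor.
- **Precision.** The view that medullary involvement has no apparent impact is one of the findings to be verified. Similar percentages without an interval cannot show how large a difference remains compatible with the data.

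At stake is whether the series can do what the Background says such a series is needed for.

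**Working it through.** The protocol has no sample size calculation to reproduce; 220 is an expected database count. It gives no event rates or follow-up times, so those below are assumptions. Prevalences come from the Background: dedifferentiation 15-25%, medullary involvement 28-48%.

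**1. Dedifferentiation scored as ever/never, outcome recurrence.** Let N = 220, overall recurrence R (assumed 20% or 30%) and ever-dedifferentiated prevalence d (15% or 25%). Assume that half of these cases are found at first diagnosis and half at recurrence. An equal split is the lower limit of the Background's statement that recurrence is the more common time. Assume also that dedifferentiation at first diagnosis has no effect on recurrence.

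- Ever group: (½·R + ½·1) = (1 + R)/2, which is 60% at R = 20% and 65% at R = 30%.
- Rest: (R − d(1 + R)/2)/(1 − d).

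| R | d | Ever group | Rest | Ratio |
|---|---|---|---|---|
| 20% | 15% | 60% (19.8/33) | (0.20 − 0.09)/0.85 = 12.9% (24.2/187) | 4.6 |
| 20% | 25% | 60% (33/55) | (0.20 − 0.15)/0.75 = 6.7% (11/165) | 9.0 |
| 30% | 15% | 65% | (0.30 − 0.0975)/0.85 = 23.8% | 2.7 |
| 30% | 25% | 65% | (0.30 − 0.1625)/0.75 = 18.3% | 3.5 |

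Counts in brackets are expected values. By construction the ratio for status at first diagnosis is 1.0, so the whole excess comes from when dedifferentiation was detected.

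**2. Medullary involvement, precision of a zero difference.** Half-width = 1.96·√(R(1 − R)(1/n₁ + 1/n₀)), with complete follow-up and the same R in both groups.

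- 28% prevalence, 62 against 158 cases, R = 20%: 1.96·√(0.16·(1/62 + 1/158)) = 0.117.
- 48% prevalence, 106 against 114 cases, R = 20%: 1.96·√(0.16·(1/106 + 1/114)) = 0.106.

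So the interval is about ±11 to 12 percentage points. At R = 10% the same groups give ±8 to 9 points, and at R = 30% ±12 to 13.5 points. Censoring would widen these.

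**3. Censoring.** Assume a constant hazard with a 10-year risk of 20%, so that the risk by time t is 1 − 0.8^(t/10). The crude percentage is then 4% at 2 years of follow-up, 11% at 5, 20% at 10 and 36% at 20, with the same underlying risk throughout. For two groups with this hazard and follow-up uniform from 0 to twice its mean, mean follow-up of 10 against 8 years gives 0.193/0.159 = 1.2, and 12 against 6 years gives 0.226/0.123 = 1.8. Equal follow-up gives 1.0.

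**The case against.** The strongest reply is that the Statistics section permits a weak analysis without prescribing one. Kaplan-Meier curves and confidence intervals are themselves descriptive, the study is a case series with no hypothesis test, and estimator, time origin and factor coding are commonly left to a statistical analysis plan, which is not at hand. This stands in part. A reader might infer that the protocol rules out time-to-event methods or plans an ever/never table; it does neither. The absence of model detail is not the point here. What remains is that the protocol's one analysis statement is weaker than its own aim, and that its own remark on timing creates a circularity it does not close.

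The Objective speaks of primary tumours, which might suggest status at first diagnosis. That word qualifies the diagnosis and does not settle when dedifferentiation is scored.

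A reader might also take the ratios in step 1 as evidence that the published prognostic effect of dedifferentiation is an artefact. They are not. The no-effect premise is only a device to isolate the bias, and the calculation covers recurrence, not survival or metastasis. Likewise, nothing in the protocol shows that follow-up differs by factor, so step 3 shows a possible distortion only.

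Finally, the interval in step 2 stays as wide after the fix. The gain is that it is reported. Possible selection through the consent rules is a separate matter, which these methods would not cure, and it carries no weight here.

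**Conclusion.** The point holds as a cheap improvement, not as an error that invalidates the study. The Statistics section could be carried out in full and leave the Objective unanswered.

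The best-grounded part is dedifferentiation. On the protocol's own prevalence and timing statement, with an equal split and no true effect, an ever/never comparison for recurrence would show a spurious ratio of 4.6 to 9.0 at an assumed 20% recurrence, or 2.7 to 3.5 at 30%. For medullary involvement, a bare statement of no impact would hide an interval of about ±11 to 12 points at an assumed 20% recurrence with complete follow-up. Distortion from unequal follow-up is possible, but its size here is unknown.

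**What to change.** Amend the Statistics section as follows.

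- Keep descriptive statistics for patient characteristics.
- For outcome by factor, report median follow-up, Kaplan-Meier overall survival, and cumulative incidence of local recurrence and of metastasis with death as a competing event, each with 95% confidence intervals.
- Classify dedifferentiation by status at first diagnosis, or treat it as time-dependent so that it counts only from the date it was found.
- Judge any statement of no impact of medullary involvement from its interval, not from similar percentages.
- If chart dates prove too incomplete, limit the Objective to description instead.

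The cost is a paragraph of wording, modest extra analysis and some date abstraction: start of follow-up, recurrence, metastasis, death, last contact, and when dedifferentiation was first found. The protocol already plans a full record review and a case report form per patient. That form is not shown, so how much of this is extra cannot be judged. No additional patients are needed, and no minimum follow-up has to be imposed. The downsides are possibly incomplete dates in old charts and intervals that will remain wide.

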### **ENROLLMENT PROCEDURE**

Patients considered eligible will be included in the study, after providing a written informed consent.

Since we will include cases of several decades ago, and due to the high incidence of mortality of the disease under investigation, it would be possible that some eligible subjects will be deceased.

### **DATA COLLECTION**

Clinical data will be retrieved by patient charts.

A protocol-specific CRF reporting the results of the review will be provided.

A CRF is required and should be completed for each included subject.

## ETHICS AND QUALITY ASSURANCE

The clinical trial protocol and its documents will be sent before initiating the study to the competent Authorities and Ethics Committees of each participating country for its approval.

The responsible investigator will ensure that this study is conducted in agreement with either the most updated Declaration of Helsinki and all the international and local laws that apply to clinical trials and to patient protection.

The protocol has been written, and the study will be conducted according to the principles of the ICH Harmonized Tripartite Guideline for Good Clinical Practice  
(ref: <http://www.emea.eu.int/pdfs/human/ich/013595en.pdf>).

## INFORMED CONSENT

All patients will be informed, by the investigator, of the aims of the study, the possible risks and benefits that will derive from the study participation. \*

The Investigator must clearly inform that the patient is free to refuse participation in the study and that can withdraw consent at any time and for any reason.

They will be informed as to the strict confidentiality of their patient data, but that their medical records may be reviewed for trial purposes by authorized individuals other than their treating physician.

The informed consent procedure must conform to the ICH guidelines on Good Clinical Practice. This implies that "the written informed consent form should be signed and personally dated by the patient or by the patient's legally acceptable representative".

The Investigator must also sign the Informed Consent form, and will keep the original at the site and a copy of the original must be handed to the patient.

The competent ethics committee for each Institution participating to the study must validate local informed consent documents before the study can be opened. It will be emphasized that the participation is voluntary and that the patient is allowed to refuse further participation in the study whenever he/she wants. This will not prejudice the patient's subsequent care.

Due to the high incidence of mortality of the disease under investigation, it would be possible that some potential eligible subjects will be deceased.

In order to allow and promote the increase in the knowledge of this rare disease that could be beneficial for other patient that are or will be affected, according to the Italian "Autorizzazione generale n. 9/2016 al trattamento dei dati personali effettuato per scopi di ricerca scientifica" of

the Privacy Tutor and the corresponding regulation in the other participating country, as well as the EU General Data Protection Regulation 679/2016 (that will be applicable from 25 May 2018), the informed consent is not required to be obtained by the deceased subjects according the aforementioned laws/dispositions.

## **CONFIDENTIALITY**

In order to ensure confidentiality of clinical trial data as disposed the national and European applicable regulation, data will be only accessible for the trial Sponsor and its designees, for monitoring/auditing procedures, the Investigator and collaborators, the Ethics Committee of each corresponding site and the Health Authority.

Investigator and the Institution will allow access to data and source documentation for monitoring, auditing, Ethic Committee revision and inspections of Health Authority, but maintaining at all times subject personal data confidentiality as specified in the "Directive 95/46/EC of the European Parliament and of the Council of 24 October 1995".

The Investigator must guarantee that patient anonymity is kept at all times and their identity must be protected from unauthorized persons and institutions.

All patients included in the study will be identified with a numeric code, so that no identifiable personal data will be collected (pseudo anonymization)

The Investigator must have and conserve a patients' inclusion registry where it figures the personal data of the patient: name, surname, address and corresponding identification code into the study, this register will be kept on the Investigator File.

## **PUBLICATION OF RESULTS**

The results from this study will be published or shown at scientific conferences.

The final publication of the study results will be written by the Principal Investigator.

## **SPONSOR ROLE AND RESPONSIBILITY**

The sponsor is the sole owner of the data and is responsible of all the clinical trial activities from study design, development, data collection, management, analysis, interpretation of data, writing and the decision to submit the report for publication written by the Principal Investigator,

